## 4. STUDY METHODS

## a. Overall study design and plan

The study was designed as a pragmatic, prospective, multicenter, cluster-randomized, crossover trial with 2x2 factorial design to evaluate four different strategies for terminal room disinfection in nine study hospitals. The 28-month study period took place from April 2012 to July 2014. The 28-month period was separated into four 7-month study periods. Each study period consisted of a 1-month "wash in" period during which hospitals implemented and refined protocols followed by a 6-month period of data collection (Figure 1).

[figure not shown]

Figure 1. Schematic of crossover design. Each institution will randomly receive four interventions over the course of the 28-month study period. The first month of each intervention will be considered a "wash-out" month and surveillance data will not be counted (black boxes).

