## b. Intervention

Each hospital will perform cleaning and disinfection of targeted rooms using four disinfection protocols: A) standard terminal disinfection using quaternary ammonium; B) enhanced disinfection with quaternary ammonium and UV device; C) enhanced disinfection with bleach; D) enhanced disinfection with bleach and UV device (Figure 2). The intervention is performed on the room. From a practical, implementation perspective, the cleaning strategies will be applied to contact precautions. From an analysis perspective, eligible rooms will include any room from which a) a patient with infection due to MRSA, VRE, CDI, or MDRAB has been transferred or discharged or b) a patient with known colonization with MRSA, VRE, and MDRAB has been transferred or discharged and c) the patient remained in the room for >24 hours prior to transfer or discharge.

Figure 2. 2x2 Factorial Design

		UV-C emitting device	
		No	Yes
Chemical Disinfectant	Quaternary ammonium- containing solution except hypochlorite (bleach)- containing solution for C. difficile rooms	Α	В
Chemical D	Hypochlorite (bleach)- containing solution	С	D

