## d. Randomization

Randomization occurred at the level of the hospital. All hospitals used each of the four strategies an equal amount of time. The order in which the four protocols were utilized was randomly assigned to each study hospital (Figure 3). Randomization was performed by random number generators for each hospital.

Hospital Study Phase 1 Study Phase 2 Study Phase 3 Study Phase 4 1 2 3 4 5 6 7 8 8 9 10 11 12 1 2 3 4 5 6 7 8 9 10 11 12 1 2 3 4 5 6 Month Year Wash In Quaternary ammomium except bleach for *C. difficile* rooms (Reference) Quaternary ammomium + UV except bleach + UV for *C. difficile* rooms Bleach Bleach + UV

Figure 3. Randomization scheme for 9 study hospitals

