#### 8. EFFICACY ANALYSES

# a. Analyses of clinical incidence - primary and secondary outcomes

Incidence rates will be compared between different disinfection protocols (study phases) using Poisson regression model with log of hospital-level number of "first positivity" cases as the outcome, log of hospital-level total days of exposure as an offset term and variables for intervention phase (B: quaternary ammonium + UV light, C: bleach, or D: bleach + UV light; A: standard disinfection will be used as reference), study period in the crossover sequence (1, 2, 3 or 4), and hospital as covariates. Interaction between intervention and study period will be evaluated. Generalized estimating equations (GEE) approach will be used to adjust for clustering by hospital. Individual models will be created for each primary and secondary efficacy outcome.

Each of the three enhanced terminal room disinfection strategies will be compared to the standard strategy; the null hypothesis in each case is that there is no difference in the clinical incidence rate between the enhanced strategy and the standard strategy. Each of the study phases will be compared to study phase A (reference) except for the patient-level analysis of *C. difficile*. As this comparison involved the comparison of bleach vs. bleach + UV-C for exposed patients, results from study phases B and D were compared to results from study phases A and C. Additional analyses will compare interventions using UV light vs those without UV light. In these analyses, variables for UV light (yes/no) and bleach (vs. quaternary ammonium) will replace the variable for intervention in the regression models.

The intention-to-treat (ITT) population will include all exposed patient stays, as described above. Per protocol (PP) population will exclude patient stays during study periods using UV light (phases B and D) if UV light was not documented as used before patient entered the room, or where the room was not in fact a seed room. For the purpose of the PP analysis, the UV device will only have to be turned on in the room; cycle completion will not be required for inclusion. Analyses of the outcomes for exposed patients will be conducted according to ITT and PP populations; analyses of the outcomes for the entire hospital will be conducted on ITT population only. Statistical tests will be performed at a two-sided significance level of 0.05 with no adjustment for multiple comparisons.

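### The additional UV/bleach model assumes one UV effect for both chemicals, and outside exposed-patient C. difficile no planned contrast gives bleach + UV versus bleach with a confidence interval

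*SAP*

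**What the plan says.** SAP Section 4a describes a "cluster-randomized, crossover trial with 2x2 factorial design to evaluate four different strategies for terminal room disinfection in nine study hospitals". Section 4b names the two bleach strategies as "C) enhanced disinfection with bleach; D) enhanced disinfection with bleach and UV device"; A and B are quaternary ammonium without and with UV. Figure 2 and the key to Figure 3 add that rooms vacated by C. difficile patients get bleach under A and B as well: the reference strategy is labelled "except bleach for *C. difficile* rooms (Reference".

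Section 8a fits a four-level intervention factor in which "A: standard disinfection will be used as reference", and states the contrasts: "Each of the three enhanced terminal room disinfection strategies will be compared to the standard strategy". The one exception is C. difficile in exposed patients, where B and D together are compared with A and C together, because for those rooms the question is bleach + UV against bleach. Additional analyses then compare UV with no UV; in these, "variables for UV light (yes/no) and bleach (vs. quaternary ammonium) will replace the variable for intervention in the regression models". No product of the two variables is mentioned. The only interaction named concerns time: "Interaction between intervention and study period will be evaluated".

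**The concern.** With one UV and one bleach coefficient on the log scale, the two-factor model forces B/A and D/C to be equal. If UV works less well where bleach is already used, which is plausible when both act on the same contamination, the single UV ratio falls between two different true values and describes neither. The plan has no formal check of this. Whether UV adds anything to bleach is the D versus C comparison, and the SAP gives it neither a test nor an interval for the exposed-patient composite (the first primary endpoint), MRSA, VRE or MDRAB, or for hospital-wide outcomes. At stake is whether a UV-versus-no-UV statement is taken to hold with both chemicals when the data support it with only one.

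**Working it through.** **Inputs from SAP Section 10a.** 7,000 exposed patients, so 7,000/4 = 1,750 per strategy; 11% outcome under A, i.e. 0.11 × 1,750 = 192.5 (the SAP writes 190); a 3-point decrease to 8%, i.e. 0.08 × 1,750 = 140; two-sided 0.05; stated power 80%.

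**Reproducing the plan's figure.** SE of log rate ratio = √(1/192.5 + 1/140) = 0.111. ln(192.5/140) = 0.318. Power = Φ(0.318/0.111 − 1.96) = 81.8%, within 2 points of the stated 80%. Independent Poisson counts are therefore a fair working model for the SAP's own planning.

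**Assumptions added.** The SAP gives no expected rates for B, C and D jointly and no intracluster correlation. The scenarios below are assumed, with equal exposure per strategy, independent counts, and no clustering or period effect. With equal exposure, the main-effects UV ratio is (B + D)/(A + C).

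**Overlap scenario: either method alone reaches 8% and both together add nothing (11/8/8/8%).** Counts: A = 192.5, B = C = D = 140.

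- Planned contrasts: B/A = C/A = D/A = 140/192.5 = 0.73, 95% CI exp(−0.318 ± 1.96 × 0.111) = 0.58 to 0.90.
- Pooled UV: 280/332.5 = 0.84; SE = √(1/280 + 1/332.5) = 0.0811; 95% CI 0.72 to 0.99; p = 0.034.
- D/C: 140/140 = 1.00; SE = √(2/140) = 0.1195; 95% CI 0.79 to 1.26. This interval is not among the planned outputs.
- Ratio of rate ratios: (D/C)/(B/A) = 1.00/0.727 = 1.375; SE = √(3/140 + 1/192.5) = 0.163; 95% CI 0.999 to 1.89; p = 0.051; power Φ(0.318/0.163 − 1.96) ≈ 50%.

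D/A and the pooled UV ratio are both nominally significant, yet UV adds nothing to bleach.

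**Other assumed patterns.**

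| Scenario (A, B, C, D) | Pooled UV (95% CI) | True B/A | True D/C | Power of product term |
|---|---|---|---|---|
| 192.5, 140, 192.5, 192.5 (bleach inert) | 332.5/385 = 0.86 (0.75–1.00) | 0.73 | 1.00 | 56% |
| 190, 133, 161.5, 161.5 | 294.5/351.5 = 0.84 (0.72–0.98) | 0.70 | 1.00 | 61% |
| 190, 133, 161.5, 133 (milder) | 266/351.5 = 0.76 | 0.70 | 0.82 | 17% |

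In the first two rows, D is worse than B: adding bleach to UV raises the rate. That is antagonism rather than overlap, so these rows are extreme cases. In the milder row, D equals B; the pooled 0.76 overstates the UV effect with bleach (0.82) only modestly and has the right direction with both chemicals.

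**Where the issue does not reach.** C. difficile rooms are bleached under all four strategies, so for exposed-patient C. difficile the B + D versus A + C comparison is itself bleach + UV versus bleach. Composite cases arising from those rooms likewise cannot have a different UV effect by assigned chemical. The scenarios above ignore this and so overstate the interaction in the composite, by an amount that depends on the C. difficile share, which the SAP does not give.

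**The case against.** The strongest reply is that the two-factor model is only an additional analysis. The main model leaves B, C and D unconstrained, and Section 11a promises estimates with 95% confidence intervals. In the overlap scenario, the table would show C/A and D/A both at 0.73, and a careful reader would see that D and C do not differ. This stands in part. A reader might infer that a UV benefit limited to quaternary ammonium will be reported as applying with bleach; the documents do not support that, because C/A and D/A remain visible and no decision rule turns the pooled ratio into a recommendation. But the reply supplies only a point estimate. D/A and C/A share arm A, so an interval for D/C cannot be read from their two intervals without the covariance.

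A second reply is that Section 8a frames its null hypotheses against the standard strategy, and that a UV effect averaged over chemicals is a legitimate estimand in a factorial trial. Both are true. The pooled analysis is not an error; the gap is that it is not labelled as an average and nothing beside it shows whether the average describes both chemicals.

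A reader might also infer that no endpoint compares bleach + UV with bleach. That is wrong for exposed-patient C. difficile, the second primary endpoint.

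**Conclusion.** The point holds in limited form. Outside exposed-patient C. difficile, the two-factor model's UV ratio rests on an unchecked assumption of equal effect with both chemicals, and D versus C has no planned interval. The consequence is a risk of misreading, not a certain false claim. Its size depends on an interaction that the SAP does not specify: under the overlap scenario, 0.84 (0.72 to 0.99) is reported where the effect with bleach is 1.00 (0.79 to 1.26); under the milder pattern, 0.76 against 0.82. Clustering is ignored throughout, and the composite is diluted by C. difficile rooms. A test of the product term would not settle the matter: it has about 50 to 61% power where UV works only with quaternary ammonium, and about 17% in the milder case. This is a cheap improvement in reporting rather than a flaw in the main comparison.

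**What to change.** Add to Section 8a, for every outcome analysed with the two-factor model except exposed-patient C. difficile:

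- From the four-level model, report with 95% CIs B vs A (coefficient β_B), D vs C (β_D − β_C) and the UV-by-chemical ratio of rate ratios (β_D − β_C − β_B).
- Present the pooled UV ratio beside these, labelled as an average over the two chemicals.
- Report all of them whatever the interaction shows. Do not let its significance decide which UV estimate supports the conclusion: in the overlap scenario p = 0.051, so a 0.05 rule would leave the pooled ratio standing.

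The four-level model already contains the interaction, so this takes contrast statements only, with no new model or data. The cost is two further unadjusted estimates per outcome (B vs A is already planned), in a plan without multiplicity adjustment, and an imprecise interaction estimate that must be read from its interval.

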## b. Alternative models

Poisson regression may not provide the best fit to the data in case of overdispersion. In addition to Poisson regression, overdispersed Poisson and negative binomial regression models will be evaluated for each outcome. Of the three candidate models, the model that has the smallest median squared deviation (squared difference between predicted and observed rate; median will be evaluated across hospitals and interventions) will be selected.

## 9. ADVERSE OUTCOMES ANALYSES

To understand if the interventions led to downstream adverse outcomes, we will analyze three potential adverse outcomes: increase in room turnover time, ER wait time, and time on diversion. In general, adverse outcomes will be described by study period using mean (standard deviation) and Median (IQR) for continuous variables and number (percent) for categorical variables. No statistical comparisons will be performed between the different study phases.

## a. Room turnover time

Total turnover time and cleaning time will be calculated using the strategy described above. Data will be obtained from environmental services logs for all rooms during each of the study periods, and the median time during the 6-month study period will be calculated. This approach will provide information on the impact, if any, of the additional time required for using the UV devices on overall environmental services operations.

# b. Emergency room (ER) wait time

ER wait time will be calculated using the strategy described above. Data will be obtained from bed flow datasets and analyzed on all patients admitted to the hospital from the ER during each 6-month study period.

## c. Time on diversion

Time on diversion will be calculated using the strategy described above. Time on diversion will be obtained from hospital operations datasets. The total time on diversion per month will be calculated for each month of each 6-month study period.

# 10. SAMPLE SIZE AND POWER CONSIDERATIONS

We performed two power calculations prior to the initiation of the study, one for the hospital-level analysis of eligible exposed patients and one for the hospital-wide analysis of all patients admitted to the hospital. Best estimates were made based on review of 4-years of surveillance data from study hospitals and published literature. Prior to our study, the proportion of new colonization/infection that occurs in rooms from which a patient with MRSA, VRE, *C. difficile*, and/or MDR-Acinetobacter was discharged is unknown. All power calculations were performed with two-sided 0.05 significance level.

- a. Eligible exposed patients Our power calculation for this analysis was based on the following assumptions. First, we projected that a total of 7,000 patients would be exposed to a seed room and eligible for inclusion in our study at the 9 study hospitals. Second, all seed rooms would be contaminated. Third, 11% of exposed, eligible patients would develop the outcome of interest. Thus, we projected that the outcome would occur in 190 (11%) of 1,750 patients during the baseline period. Based on these assumptions, our study had 80% power to detect an absolute decrease in the proportion of outcomes caused by the four target organisms of 3% for any of the enhanced disinfection strategies and >99% power to detect an absolute decrease of 5% or more.
- b. **Hospital-wide** Our power calculation for this analysis was based on the following assumptions. First, we projected that 1.96 million patient days of care would be provided at the 9 study hospitals during the study period. Second, for each 6-month intervention period, we projected that approximately 491,200 patient-days of care will occur (distributed across 9 participating hospitals). Third, we projected that 959 outcomes due to the four target organisms would occur during the baseline (or reference) 6-month period, for a baseline incidence rate of 1.95/1,000 patient-days. Under these assumptions, the study had 60% power to detect a 10% decrease in incidence rate, 92% power to detect a 15% decrease and >99% power to detect a 20% decrease.

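### The hospital-wide powers in Section 10b assume that all events are independent and have about one point of slack; hospital-period variation and the planned period adjustment are not allowed for

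*SAP*

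**What the plan says.** Section 10 gives two power statements, both under one rule: "All power calculations were performed with two-sided 0.05 significance level".

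- **Hospital-wide (10b).** The first input is exposure time: "for each 6-month intervention period, we projected that approximately 491,200 patient-days of care will occur (distributed across 9 participating hospitals"). The second is the event count: "we projected that 959 outcomes due to the four target organisms would occur during the baseline (or reference) 6-month period". Together they make a reference rate of 1.95 per 1,000. The power statement reads: "Under these assumptions, the study had 60% power to detect a 10% decrease in incidence rate, 92% power to detect a 15% decrease". For a 20% decrease the stated power exceeds 99%. Section 3b lists hospital-wide incidence as secondary.
- **Exposed patients (10a).** This is the population of the primary endpoints. With 11% of 1,750 patients per strategy having the outcome, "our study had 80% power to detect an absolute decrease in the proportion of outcomes caused by the four target organisms of 3" percentage points, and more than 99% power for 5 points.

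Neither list of assumptions contains an intracluster or between-period correlation, a coefficient of variation, a dispersion factor or a design effect. The nine hospitals enter the hospital-wide list only as the places that supply the patient-days.

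Elsewhere the SAP describes a different structure. Section 4d randomises the order of strategies by hospital. Section 8a models hospital-level counts with strategy, study period and hospital terms, and uses GEE for clustering. Section 8b says "Poisson regression may not provide the best fit to the data in case of overdispersion" and adds overdispersed Poisson and negative binomial models as candidates.

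**The concern.** The power section describes a simpler comparison than the one Section 8 plans. Each strategy contrast rests on nine pairs of hospital-periods. If a hospital's rate moves from one six-month period to the next for reasons other than the strategy (outbreaks, testing practice, case mix), that movement adds to the error of the contrast. More patient-days in the same nine hospitals do not remove it. A calculation on total events leaves it out.

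What is at stake is interpretation. A null hospital-wide result set beside 92% power reads as good evidence against a 15% decrease. If the true power is nearer 70% or 50%, it is not.

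**Working it through.** **1. Reproducing the hospital-wide figures.** Inputs from Section 10b: E1 = 959 events on the reference strategy and E2 = 959 × RR on the comparator, with equal patient-days (959/491,200 = 1.952 per 1,000, as stated). For independent Poisson counts,

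power = Φ( −ln RR / √(1/E1 + 1/E2) − 1.96 ).

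| Decrease | −ln RR | Standard error | Ratio | Power | Stated |
|---|---|---|---|---|---|
| 10% | 0.1054 | 0.0469 | 2.246 | 61.2% | 60% |
| 15% | 0.1625 | 0.0476 | 3.411 | 92.7% | 92% |
| 20% | 0.2231 | 0.0484 | 4.607 | 99.6% | >99% |

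Other two-sided calculations with independent events, including two proportions on patient-days, give 61.2–61.4%, 92.7–92.8% and 99.6%. A one-sided test does not fit (72.6% and 96.1% for the first two). What the matching calculations share is independence of events, not the Poisson form in particular.

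**2. Adding hospital-period variation.** Assumption: rates vary between hospital-periods beyond Poisson with coefficient of variation c. Averaged over nine hospitals on each side of the contrast, this adds 2c²/9 to the variance of the log rate ratio. Stable differences between hospitals are not charged, because the crossover removes them.

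| c | 10% decrease | 15% | 20% |
|---|---|---|---|
| 0 | 61.2% | 92.7% | 99.6% |
| 0.02 | 59.5% | 91.7% | 99.5% |
| 0.03 | 57.5% | 90.5% | 99.3% |
| 0.05 | 51.9% | 86.4% | 98.5% |
| 0.10 | 35.4% | 67.9% | 91.0% |
| 0.15 | 23.6% | 47.9% | 74.0% |

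The loss is steep because a hospital-period averages 959/9 ≈ 107 events, so Poisson noise alone has a coefficient of variation of 1/√107 ≈ 0.10. Extra variation of the same size doubles the variance: 1 + 0.10² × 959/9 = 2.07.

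**3. The planned model with no extra variation.** Take nine equal hospitals, each with an independently randomised order of the four strategies, and the hospital + period + strategy Poisson model of Section 8a. The model has 9 + 3 + 3 = 15 parameters on 36 hospital-periods, which leaves 21 degrees of freedom. Taking the variance of the strategy coefficient from the expected information, and averaging power over random orders, gives about 56%, 89% and 99% with a normal reference and 52%, 86% and 98% with t on 21 df. The loss arises because random orders over nine hospitals leave strategy and period partly confounded. Roughly one order in ten still reaches 60% for a 10% decrease.

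A simulation of the same model (600 runs per cell, quasi-Poisson t test) agrees: 50%, 87% and 99% at c = 0; 31%, 61% and 86% at c = 0.10; 12%, 27% and 50% at c = 0.20.

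**4. Exposed patients, 11% to 8%, 1,750 per strategy.**

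- Poisson counts, 192.5 against 140 events: ln(192.5/140) / √(1/192.5 + 1/140) = 0.3185/0.1111 = 2.867, so power is 81.8%.
- Two proportions: 0.03 / √((0.11 × 0.89 + 0.08 × 0.92)/1,750) = 0.03/0.0099 = 3.030, so power is 85.8% (85.7% with pooled variance, 84.4% with continuity correction).

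Hospital-period variation adds 2c²/9 to the first variance, and c²(0.11² + 0.08²)/9 to the second.

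| c | Poisson counts | Two proportions |
|---|---|---|
| 0 | 82% | 86% |
| 0.10 | 75% | 79% |
| 0.15 | 68% | 71% |
| 0.20 | 59% | 61% |

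On the proportion scale, 80% is reached at c ≈ 0.09. With 192.5/9 ≈ 21 events per hospital-period, sampling noise is larger and extra variation matters less.

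**The case against.** The strongest reply is that no sum is wrong. The hospital-wide sentence is conditional on its listed assumptions and reproduces from them. The SAP gives no value of c, and its mention of overdispersion is a contingency, not evidence. The crossover removes stable hospital differences, so randomising hospitals does not by itself cost power. The figures concern a secondary endpoint, were computed before the study began, and change no estimate or test. Section 11a commits to 95% confidence intervals, which carry the precision actually achieved.

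Much of this stands, and it rules out three stronger readings that a reader might infer.

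- **That the design certainly fails to deliver the stated powers.** The size of any loss through c rests on an undocumented value. The loss from period adjustment depends on the realised orders in Figure 3, which were not available to this check. With a favourable order and negligible c, the figures could hold. The claim for a 20% decrease is the most robust: 98.5% at c = 0.05 by the simple formula.
- **That the figures rest specifically on a Poisson assumption.** Independent proportions give the same hospital-wide values.
- **That the exposed-patient 80% also ignores clustering.** That statement is framed as a difference in proportions, and 80% lies below the 86% that independent proportions give. An allowance can be neither shown nor excluded.

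What the reply does not answer is the lack of slack. The independence result exceeds the stated 60% and 92% by about one point, so no meaningful allowance can be hidden in them, and c = 0.02 already takes both below the stated values. Confidence intervals reduce the risk of misreading a null result but do not correct a stated power.

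**Conclusion.** The point holds for the hospital-wide figures in Section 10b. They reproduce under independent events, and they allow neither for hospital-period variation nor for the period adjustment in the planned model. By the simple formula, the stated 60% and 92% need c below about 0.02. At an assumed c of 0.05 to 0.15, power is 52% down to 24% for a 10% decrease and 86% down to 48% for a 15% decrease. In the planned model with c = 0, equal hospitals and independently randomised orders, it averages about 56% and 89%, or 52% and 86% with t on 21 df.

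For the exposed-patient 80%, a shortfall is conditional on c: below about 0.09 there is none if the calculation was a simple comparison of two proportions. The defect there is that the method is not stated.

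This is an omitted assumption in a planning statement. It is worth correcting before the power is cited, but it does not threaten the validity of the analysis.

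**What to change.** 1. In Section 10b, label 60%, 92% and >99% as assuming independent events.
2. Estimate c, the variation between six-month periods within hospital beyond Poisson, from the four years of surveillance data that Section 10 cites.
3. Restate both power statements for the hospital + period + strategy model, using the actual allocation of orders, over c from 0 to 0.15 with the estimate marked.
4. In Section 10a, state the method behind the 80%, including whether clustering was allowed for.

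The cost is a short calculation on data already in hand and some wording in the SAP and manuscript. The number of hospitals, the periods and the analysis stay as they are. The only downside is that the stated power becomes less favourable.
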